Finally, as it is an educational strategy, the population that a priori benefits the most from these interventions is the personnel in training. In the case of the Faculty of Medicine of the University of Antioquia, the training of non-technical skills is not included in the micro curriculum of critical patient care, therefore, the results of the present study could be used to define modification or confirmation of the micro curriculum for critical patient care in the last semester of medicine.

6b. Comparison justification.

Until now, the use of checklists is the intervention that has the most empirical support in reducing medical error due to omission of steps in surgery (38). Arriaga et al. Found that the use of checklists reduces simulation crisis medical error with an absolute risk reduction of 17% and relative risk of 0.28. IC0.18 to 0.42; P < 0.001(27). Finally, in the clinical trial by Duclos et al., In which checklists versus MRC training plus checklists were compared, a decrease in adverse event was shown in the two groups without differences between them, 8.8 to 5.5% (OR 0.57, 95% CI 0.48 to 0.68) versus 7.9 to 5.4% in control (OR 0.64, 0.50 to 0.81) (ROR 0.67 to 1.21)(31); the authors attribute the decrease in the probability of an adverse event to the application of checklists.

In light of this, the checklist is the best strategy to prevent medical error in omitting steps in crisis, which is why the World Health Organization WHO recommends the use of checklists to reduce medical error in surgery. and medication error; and further recommends them as a primary educational component in patient safety competencies.

Research question

In the last semester medical students at the University of Antioquia, does training in nontechnical skills and checklists reduce simulation crisis medical error, compared to training with checklists?

7. Objectives and Hypotheses

Hypothesis

In the last semester of medicine students at the University of Antioquia, training of nontechnical skills and checklists is superior compared to conventional training with checklists to decrease at least 10% omission of steps in crisis management medical in high fidelity simulation.

Primary objective

To determine if the training of non-technical skills and checklists in final semester students of medicine at the University of Antioquia is superior to conventional training with checklists

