to decrease at least 10% of omission of steps in the management of medical crisis in high fidelity simulation.

Secondary Objectives

Determine if there are differences between intervention and control strategies in the following results:

Crisis resolution time Time in detection and discrimination of the crisis Overall score of non-technical skills Discriminated score between dimensions of non-technical skills Student satisfaction Incidence of inadequate crisis management

8. Study design:

TECRISIS is a study designed as a controlled clinical trial of superiority with parallel groups, random allocation and blinding of investigators who measure outcome.

III Methods: participants, interventions and outcomes

9. Description of the study characteristics

Reference population: medical students

Study population: final semester students of medicine at the University of Antioquia. This study will be carried out in Medellín Colombia, in a single center, the University of Antioquia. This center is chosen since it has a high fidelity simulation center, teachers with simulation experience and also has more than 100 medical students per semester. The community of students of the last semester of medicine is chosen since they are the population to which the possible results of the present study may have better application. Additionally, these interventions are educational strategies and could be adjusted or included in the institution's undergraduate medical curriculum program.

10. Eligibility criteria

10a. Inclusion criteria

• Older than 18 years-old.

- Final semester student of medicine at the University of Antioquia.
- Have passed the theoretical knowledge exam for handling crisis events with a score of 100%
- On-site availability for training days

10b. Exclusion criteria

- Have received training in a specific crisis resource management course.
- Refusal to participate in the clinical study.

11a. Interventions

For all study participants:

In order to increase homogeneity in the technical concepts prior to the interventions, all the participants will take a theoretical knowledge test to manage the events of the following crises: anaphylaxis, unstable bradycardia, cardiac arrest with defibrillable and non-defibrillable rhythms, airway management failure, bronchospasm, severe bleeding, low blood pressure, hypoxia, and unstable tachycardia.

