The proportion of treatment steps and not the incidence of medical error is taken as the unit of analysis, the reason for this is the high incidence of medical error that can even manifest itself with more than one error due to crisis, therefore, if used the incidence of the event would decrease the sample size.

Based on the study by Arraiga et al., The proportion of missed treatment steps in the expected control group is 26% and we consider a further 10% reduction in the intervention group to be clinically important. A minimum of 10% additional reduction in omitting treatment steps is decided because it is the approximate effect size of the other dimensions of non-technical skills other than resource management, a dimension that includes the use of checklists. It also establishes power of 90% and alpha of 0.05.

The sample calculation is then carried out in the analysis unit omitting treatment steps according to the formula:

$$n = \frac{\left[Z_{*} * \sqrt{2p(1-p)} + Z_{p} * \sqrt{p_{1}(1-p_{1}) + p_{2}(1-p_{2})}\right]^{2}}{(p_{1}-p_{2})}$$

With the statistical program R version 4.0.0 epiR statistical package, with the following code:

> library (epiR)

> epi.propsize (treat = 0.16, control = 0.26, n = NA, power = 0.9, design = 1, sided.test = 2, conf.level = 0.95)

We found a sample size of 492 treatment actions per arm, which corresponds to 984 in total, and with an estimate of student losses of 20%, we found the total of 1,180 treatment actions; Since 21 treatment steps are evaluated in each team, we obtain a total of 56 final semester medical students, 28 in each arm.

15. Recruitment

In order to complete the calculated sample size, the following recruitment strategies will be carried out:

- Explanation of the project at least once per internship cohort with the whole group.
- Request for participation on day 1 of the anesthesiology rotation in boarding school and the care rotation of the critically ill patient.

Table 8. Monthly evaluation of the monitoring status

Recruitment month	one	2	3	4	5	6	7	8
Current current income								
Income to date								
Income goal to date								
Real less projected								
Success ratio								
Projected final income								
Final deficit or excess								

IV Methods: allocation of interventions

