The analysis of each variable is explained in Table 9, prior to the use of parametric tests, the necessary assumptions will be verified including probability distribution tests, independence of the data and equality of variances according to the case. For the ratio of proportions and mean differences of the groups, in case of non-compliance, non-parametric statistical inference will be made.

To compare the intervention arm: training with non-technical skills and checklists with the control group: training with checklists, the proportion of omission of treatment steps per group will be used as the primary outcome variable.

Alternate hypothesis: the difference in the proportion of omission of treatment steps between the control and intervention group is greater than 10%.

Null hypothesis: the difference in the proportion of omission of treatment steps between the control and intervention group is 10% or less.

Table 9 analysis plan by variable

Outcome	Outcome	Statistical	Estimator	Analysis
	measure	hypothesis		method
Primary outcome: Medical error	Ratioofomissionoftreatmentstepsto totalstepsgroup.	Ha: Pcontrol - P intervention> 10% HO: Pcontrol - Intervention = 10%	Difference in proportions (95% CI)	Chi square test
Overall score on non-technical skills scale	Average Interval per group between 1 to 45	He has: µintervention>µcontrol Ho: µintervention≤ µcontrol	Mean difference (95% Cl)	T Student test.
Ottawa Leadership on Scale	Average Interval per group between 1 and 7	He has: µintervention>µcontrol Ho: µintervention≤ µcontrol	Mean difference (95% CI)	T Student test.
Ottawa scale problem solving	AverageIntervalpergroupbetween 1 and 7	AverageIntervalper groupbetween1 and 7	Mean difference (95% CI)	T Student test.
Situational awareness on the Ottawa scale	AverageIntervalpergroupbetween 1 and 7	Hehas:µintervention>µcontrolHo:µintervention≤µcontrol	Mean difference (95% CI)	T Student test.
Utilization of Ottawa scale resources	Average Interval per group between 1 and 7	He has: µintervention>µcontrol Ho: µintervention≤ µcontrol	Mean difference (95% CI)	T Student test.
Ottawa Scale Communication	Average Interval per group between 1 and 7	He has: µintervention>µcontrol Ho: µintervention≤ µcontrol	Mean difference (95% CI)	T Student test.
Crisis resolution time	Average time in minutes per group	He has: µintervention< µcontrol Ho: µintervention≥ µcontrol	Mean difference (95% CI)	T Student test.

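### The primary null is a reduction of 10 points or less, but the chi-square and the sample size both address zero, so a significant result would not support the stated claim and the 90% power does not apply to it

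*Combined protocol and SAP*

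**What the plan says.** **Section 20a (text).** The null is "Null hypothesis: the difference in the proportion of omission of treatment steps between the control and intervention group is 10% or less"; the alternative is a difference above 10%.

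**Table 9, primary outcome.** The alternative is "Ha: Pcontrol - P intervention> 10"% and the null is "HO: Pcontrol - Intervention = 10"%. The estimator is "Difference in proportions (95% CI") and the method is a chi-square test. No shifted null is given, and nothing says how the interval is to be compared with 10.

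**Section 14.** The expected control proportion is 26%, with power 90% and alpha 0.05. The code uses "treat = 0.16, control = 0.26, n = NA, power = 0.9, design = 1, sided.test = 2, conf.level = 0.95" and has no margin argument. On the choice of effect: "A minimum of 10% additional reduction in omitting treatment steps is decided". The stated result is 492 steps per arm, raised for 20% losses to 56 students (28 per arm) with 21 steps each.

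**Section 7.** The hypothesis is that the intervention is superior "to decrease at least 10% omission of steps in crisis management medical in high fidelity simulation". The primary objective says the same: "to decrease at least 10% of omission of steps in the management of medical crisis in high fidelity simulation".

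**The concern.** Two different hypotheses are in use. Section 20a and Table 9 put the null at 10 points. The named test and the sample-size code put it at zero and treat 10 points as the true effect.

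Section 7 adds a conflict at the boundary. A true reduction of exactly 10 points meets its objective of at least 10%, yet section 20a places that value inside the null. It is also the effect the trial is sized to detect.

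The trial's main claim is at stake. If the chi-square decides the primary hypothesis as Table 9 has it, p < 0.05 would be taken as rejecting a reduction of 10 points or less, when it shows only a difference from zero. The background section says the results may be used to change or confirm the critical-care curriculum, so evidence of some reduction should not be reported as evidence of more than 10 points.

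**Working it through.** **Inputs.** Control proportion 0.26, planned intervention proportion 0.16, two-sided alpha 0.05, 492 steps per arm, 21 steps per student, 28 students per arm and 20% loss (all section 14). Steps per arm therefore run from 28 × 0.8 × 21 = 470.4 (full losses) to 28 × 21 = 588 (none). Steps are treated as independent, as section 14 does. True reductions other than 10 points are my assumptions; the documents give none.

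**1. The plan's own figure.** Against a null of zero, with mean proportion 0.21:

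n = [1.960·√(2·0.21·0.79) + 1.282·√(0.26·0.74 + 0.16·0.84)]² / 0.10² ≈ 347 per arm.

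The stated 492 is not reproduced at alpha 0.05; two-sided alpha 0.01 gives exactly 492. This is a separate error and does not affect the present point, since both calculations are against zero. At 492 per arm the chi-square has about 97% power for a true 10 points.

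**2. How often the chi-square rejects when the stated null is true.** Power = Φ[(d − 1.960·SE₀)/SE₁], with SE₀ pooled and SE₁ unpooled. For d = 0.05 and n = 492, SE₀ = 0.02703 and SE₁ = 0.02699, giving 0.456.

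| True reduction | 470 steps/arm | 492 | 588 |
|---|---|---|---|
| 5 points | 44% | 46% | 53% (0.525) |
| 8 points | 84% | 86% | 91% |

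Simulation with 400,000 runs at 5 points gave 0.441, 0.457 and 0.526.

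**3. Observed reduction needed** (control at 26%).

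| Criterion | 470 | 492 | 588 |
|---|---|---|---|
| Chi-square p < 0.05 | 5.4 points | 5.3 | 4.9 |
| Lower 95% limit above 10 | 14.9 points | 14.8 | 14.4 |

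**4. Power of a test that does address the 10-point null.** Requiring the lower limit of the two-sided 95% CI to exceed 10 is a one-sided test at 0.025: power = Φ[(d − 0.10)/SE₁ − 1.960]. At d = 0.10 the first term is zero, so power is Φ(−1.960) = 2.5% at any n.

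| True reduction | 470 | 492 | 588 |
|---|---|---|---|
| 10 points | 2.5% | 2.5% | 2.5% |
| 12 points | 12% | 12% | 14% |
| 15 points | 52% | 54% | 61% |
| 18 points | 92% | 93% | 96% |

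**5. Size for 90% power against the 10-point null.** n = (1.960 + 1.282)²·[p_c(1 − p_c) + p_i(1 − p_i)]/(d − 0.10)².

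- d = 0.12: variance sum 0.1924 + 0.1204 = 0.3128, giving n = 8,217 steps, or 392 students per arm.
- d = 0.15: variance sum 0.1924 + 0.0979 = 0.2903, giving n = 1,221 steps, or 59 students per arm.
- d = 0.18: variance sum 0.1924 + 0.0736 = 0.2660, giving n = 437 steps, or 21 students per arm.

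**6. Sensitivity to clustering.** The documents give no within-student correlation. Assuming an ICC of 0.02 to 0.10, the design effect is 1 + 20·ICC = 1.4 to 3.0. The observed reduction needed for the lower limit to pass 10 becomes 15.1-18.1 points. Margin-test power falls to 21-48% at a true 15 points and 49-89% at 18.

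**The case against.** The strongest reply is that this is a wording slip and no margin design was meant. Section 8 calls the trial a superiority study, the research question asks only whether training reduces error, and section 14 treats 10 points as the clinically important difference, with no margin in the code. The target difference was probably carried into the hypotheses by mistake. That reading is likely right, and the recommended fix adopts it. It does not remove the problem, because the 10% stands in the hypothesis, the primary objective, section 20a and Table 9, and on that text a significant chi-square supports the larger claim.

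Second, Table 9 plans a 95% CI, so a reader would see a lower limit below 10, and the plan nowhere says in words that p < 0.05 will be read as rejecting the margin. This lessens the risk of misreading. But no rule ties the interval to 10, and the chi-square is the only method named for the primary hypothesis.

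Third, the margin figures depend on sidedness. Table 9's primary alternative is directional; a one-sided 0.05 test would give 5% power at a true 10 points, 64-73% at 15, and a requirement of about 995 steps (48 students) per arm at 15. I used 0.025 in one direction because section 14 specifies a two-sided 0.05 and Table 9 a 95% CI. The conclusion is the same either way.

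The null written with an equals sign in Table 9 is ordinary shorthand and would not matter on its own.

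**Conclusion.** The concern holds and should be corrected before any data are seen. As written, the primary test does not address the stated primary null, and the 90% power belongs to a different hypothesis. For the stated hypothesis, power at the planned effect equals the one-sided error rate, 2.5%, and enlarging the trial cannot change that. Read against the stated null, the chi-square would reject wrongly 44-53% of the time at a true 5 points.

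That the test and the sizing address zero, and that power at the boundary equals alpha, follow from the documents alone. The other percentages rest on the 26% control rate, 470-588 steps per arm, independent steps and the true reductions I assumed. Positive correlation of steps within a student would lower the margin-test power further.

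**What to change.** **Recommended.**

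- In section 20a and Table 9, set H0: Pcontrol − Pintervention = 0 against Ha: not equal to 0, two-sided alpha 0.05. This is what the chi-square and the sample-size code address.
- Keep 10 points as the planning effect and the benchmark of clinical importance, and reword the hypothesis and primary objective in section 7 to match.
- Add one rule: a reduction of at least 10 points is claimed only if the lower limit of the planned 95% CI exceeds 10.
- Use the same variance method for the test and the CI. If one allows for steps clustered within student, so must the other.

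This changes text only and needs no extra participants. The headline claim becomes that training reduces omissions, without the 10-point qualifier. At a true reduction of exactly 10 points, the added rule would be met only 2.5% of the time, so the stronger claim should not be expected at the planned effect. Because the objective changes, section 25 requires a formal correction and ethics approval if the protocol is already approved; Table 1 lists the study as still at the protocol-writing stage.

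**Alternative, if the 10-point margin is meant as the primary claim.** Test it directly (lower CI limit above 10), treat exactly 10 points the same way in section 7, section 20a and Table 9, withdraw the 90% power at 26% versus 16%, and re-size for a stated true effect above 10 points. Even at a true 15 points with independent steps, this needs about 59 students per arm before losses, against 28 planned.

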Annex 1: List of medical crises with their corresponding treatment steps.

Air Embolism	1. Declare the crisis
	2. Request Help in less than 1 minute
	3. Apply FiO2 100%
	4. Stop the air intake site by applying
	irrigation
	5. Request echocardiography
	6. Start dobutamine or norepinephrine if
	hypotension in less than 2 minutes
	7. Position in lateral decubitus on the
	affected side before 10 minutes
Anaphylaxis	1. Declare the crisis
	2. Request help in less than 1 minute
	3. Apply FiO2 100%
	4. Stop infusions
	5. Apply IM or IV adrenaline in less than 2
	minutes
	6. Apply infusion epinephrine in case of
	non-response of 1 to 4 micrograms /
	minute
	7. Apply Hydrocortisone 100-200mg IV
	within 10 minutes
Unstable Bradycardia	1. Declare the crisis
	2. Request Help in less than 1 minute
	3. Apply FiO2 100%
	4. Apply atropine 0.5mg IV repeat up to
	3mg total dose

	 5. Use adrenaline 2ugr / min after atropine failure until capture of transcutaneous pacemaker 6. If bradycardia persists use transcutaneous pacemaker 7. Increase 10mA until presence of pulse
Cardiac arrest / Asystole (hypoxemia)	 Declare the crisis Request Help in less than 1 minute Apply FiO2 100% Start cardiac massage in less than 1 minute Apply 1mg adrenaline every 3 to 5 minutes Rhythm detection every 2 minutes Placement of advanced airway device less than 5 minutes
Cardiac Arrest / Ventricular Tachycardia	 Declare the crisis Request Help in less than 1 minute Apply FiO2 100% Start cardiac massage in less than 1 minute Apply 1mg adrenaline every 3 to 5 minutes Rhythm detection every 2 minutes Application of electric shock with 200J bipolar in less than 3 minutes
Unanticipated difficult airway	 Declare the crisis Request Help in less than 1 minute Apply FiO2 100% Perform minimum 3 laryngoscopies maximum 4 Use second-generation supraglottic after laryngoscopy failure Stop airway interventions after rescue with supraglottic Application of neuromuscular relaxant at full dose (rocuronium 1.2 mg / kg dose or succinylcholine at 1.5mg IV)
Hypovolemic shock from open trauma	 Declare the crisis Request Help in less than 1 minute Apply FiO2 100% Verify the patency of 2 peripheral veins

Distributional shock hypotension	 5. Administer 20ml / kilo bolus of crystalloids in less than 5 minutes 6. Request bulk transfer package 7. Repeat 20ml liquid bolus / crystalloid thread 1. Declare the crisis 2. Request Help in less than 1 minute 3. Apply FiO2 100% 4. Apply 20ml / kilo crystalloid bolus in the first 5 minutes 5. Start norepinephrine at a dose of 0.05ug / k / min in less than 5 minutes
	6. Request vital signs monitoring every 5minutes7. Verify patency of 2 venous accesses
Malignant hyperthermia	 Declare the crisis Request Help in less than 1 minute Apply FiO2 100% Apply Dantrolene at a dose of mg / kg in less than 5 minutes Increase ventilatory minute volume to Min Suspend possible triggers of the crisis Apply topical cooling measures
Foreign body airway obstruction	 Declare the crisis Request Help in less than 1 minute Apply FiO2 100% Apply support with positive pressure ventilation in less than 4 minutes Manual removal of foreign body in less than 5 minutes Indicate safety position in right lateral decubitus after removal of foreign body Assess consciousness using the Glasgow scale application.
Unstable ventricular tachycardia	 Declare the crisis Request Help in less than 1 minute Apply FiO2 100% Request stop car in less than 1 minute Cardiovert in synchronous mode with 100 Joules in the first 3 minutes Perform second cardioversion with 150 Joules in the first 5 minutes

7. Request control electrocardiogram after return to sinus rhythm

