10 hour program; two hours on the teleeducation platform that includes a description of the checklists to be used, reflection exercises with a previous test and a test at the end of the contents of the platform focused on checklists; and 8 face-to-face hours in high-fidelity simulation divided into two four-hour days with a minimum of three days of difference between them, in which directed and structured reflection (structured debriefing) will be emphasized to the mental models that are related to the checklists. In crisis.

The training will be carried out with four random crises from the list of the pathologies described, two in each session, this in order to avoid cognitive continuity bias.

To achieve the correct use of the checklist in crisis, directed and structured reflection will be carried out so that the participants acquire the following behaviors

- Choosing the right list for the stage
- Assignment of a specific participant using the checklist
- Feedback to the work team on each action suggested in the checklist

For the present protocol, the checklists in Spanish of the Colombian Society of Anesthesiology SCARE that are freely available will be used during the development of simulation crises.(41).

Recording for measurement of outcomes:

The measurement of the outcomes described in section 18, will be carried out after completing the training, on a day different from the last simulation session. To guarantee the homogeneity of the treatment teams, each participant will be evaluated separately in a group of four people where three are resident doctors trained in non-technical skills and checklists blinded to the intervention, since they do not participate in the training sessions. , who will assume the roles of two nursing assistants and a circulator.

Three crises will be carried out at random, different from those used in training to avoid cognitive continuity bias and will be recorded in the same simulation center for all participants with a Logitech[®] brand HD camera reference Pro stream C922 using a Jabra brand microphone [®] reference Speak 510Ms.

For all cases after recording for outcome measurement:

As the intervention and control are about educational strategies of problem solving skills in medical crises, in simulated environments in students from the same year of training, from

a single center, in which it is not possible to blind the participant, there may be communication between treatment and control groups.

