As the teaching-learning relationship is bidirectional, other educational interventions on technical skills related to the scenarios and the resolution of questions and doubts about the technical concepts related to the platform will be allowed for both groups.

No training will be conducted in either group on non-technical skills other than those contained in the training in this protocol.

12. Outcomes

12.1 Primary outcome:

Difference of proportions of omission of steps to treatment by group, the measurement of this outcome will be made by reviewing the recordings of three random medical crises different from those used for training in each group of participants. The evaluation will be done by an independent collaborator blinded to the intervention group and previously trained in the detection of errors by one of the authors. Failure to apply the specific actions defined in each pathology, chosen by the authors according to Annex 1, will be considered as omission of the treatment step, this includes the maximum time determined for each action, the choice of appropriate medications with their respective doses, among others. Each evaluation is independent, each crisis will be evaluated in seven steps,

12.2 Secondary outcomes:

12.2a 1Difference of crisis resolution time averages in seconds between both groups, measured in the recording, taking as the beginning of the crisis the moment of calling the treatment team and the end when all the effective treatment of each crisis is completed, according to the treatment steps described in Annex 1. In the event that the treatment steps are not fully completed, the time will be measured until the end of the simulation.

12.2b Difference of time averages in detection and discrimination of the crisis in seconds between both groups, taking as the beginning of the crisis the moment of calling the treatment team and the end the moment of explicitly requesting the specific checklist for the crisis or verbalize the diagnosis of the code situation. If the specific list is not requested or the diagnosis is not verbalized, the time until the end of the simulation will be counted.

12.2c Mean difference between the global non-technical skills score measured with the Ottawa global scale based on video recording by an independent evaluator.

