Cardiac arrest / Asystole (hypoxemia)	 Start cardiac massage in less than a minute Apply 1mg adrenaline every 3 to 5 minutes Use of advanced airway device in less than 5 min
Cardiac Arrest / Ventricular Tachycardia	 Start cardiac massage in less than 1 minute Rhythm detection every 2 minutes Application of electric shock with 200J bipolar in less than 3 minutes
Unanticipated difficult airway	 Apply FiO2 100% Perform minimum 3 laryngoscopies maximum 4 Use second-generation supraglottic after laryngoscopy failure
Hypovolemic shock from open trauma	 Verify the patency of 2 peripheral veins Administer 20ml / kilo bolus of crystalloids in less than 5 minutes Request Mass Transfusion Package
Distributional shock hypotension	 Apply 20ml / kilo crystalloid bolus in the first 5 minutes Start norepinephrine at a dose of 0.05ug / k / min in less than 5 minutes
Malignant hyperthermia	 Apply Dantrolene at a dose of mg / kg in less than 5 minutes Suspend possible triggers of the crisis
Foreign body airway obstruction	 Apply FiO2 100% Apply support with positive pressure ventilation in less than 4 minutes Manual removal of foreign body in less than 5 minutes
Unstable ventricular tachycardia	 Cardiovert in synchronous mode with 100 Joules in the first 3 minutes Perform second cardioversion with 150 Joules in the first 5 minutes

13. Figure 2: Participants timeline

[figure not shown]

Table 7. Follow-up program and procedures

	Reclu	Assign					D	. +	211		tion	stage				Closir	20
Time in days					1	1	P	551-	alli	JLa	1	eleve	1	1	1	fiftee	ושי 1
Time in days	one	one	2	3	4	5	6	7	8	9	_		_	_	_		
Exercise																	
Assignment																	
Allocation screening																	
Theoretical knowledge test																	
Informed consent																	
Assignment																	
Intervention																	
Post-test virtual platform																	
HNT and LC training																	
LC training																	
Evaluations																	
Baseline measurement																	
Recording of outcome crisis																	
Outcome measurement																	
Measurement of secondary																	
outcomes																	

Reclu: Recruitment, Assig: Assignment.

14. Sample Size

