Data will not be presented masked to the external data monitoring committee.

17b. Circumstances to reveal masking.

It will be considered to reveal the masking of the outcome in the event that any of the participants present at the time of recording for the measurement of the outcome great psychological or emotional affectation by the simulation and the safe container described in the simulation methodology is not enough.

V Methods: data collection, management and analysis.

18. Baseline and outcome data collection plan

Baseline characteristics: the following baseline characteristics of the participants in the first simulation session will be collected: age, sex, personal history of sleep disorders, personal history of mood disorders, hours of weekly care rotation, hours of daily sleep on average, reported simulation training hours, weekly work hours if applicable. On the day of the outcome measurement, the variable hours of sleep the day before the outcome measurement will be recorded. The variables to be registered are discriminated in Annex 5.

These data will be filled out in physical form and will be transcribed in a database in Google documents.

The outcome variables will be carried out electronically and are summarized in Table 8.

Outcome	Measurement	Responsable	
Primary			
Skipping treatment steps	Electronic format in Google	Blind collaborator to the	
	based on video recording.	intervention	
	Secondary		
Crisis resolution time	Electronic format in Google	Blind collaborator to the	
	based on video recording.	intervention	
Time in detection and	Electronic format in Google	Blind collaborator to the	
discrimination of the crisis	based on video recording.	intervention	
Overall score of non-technical	Electronic format in Google	Blind collaborator to the	
skills	based on video recording.	intervention	
Discriminated score between	Electronic format in Google	Blind collaborator to the	
dimensions of non-technical	based on video recording.	intervention	
skills			
Student satisfaction	Electronic version of Format	Self completed by the	
	F-025-08 of the Simulation	Student in an anonymous	
	Center, Faculty of Medicine,	format.	
	University of Antioquia		
Incidence of inadequate crisis	Electronic format in Google	Blind collaborator to the	
management	based on video recording.	intervention	

Table 8 measurement of outcome variables

18b. Plan to promote retention and complete follow-up

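### Annex 1, difficult-airway step 7, gives rocuronium per kilogram but succinylcholine as a bare 1.5 mg: a minor unit correction to the primary-outcome scoring key

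*Combined protocol and SAP*

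**What the plan says.** Section 12.1 defines the primary outcome as the difference in the proportion of omitted treatment steps. It names Annex 1 as the list of required actions, seven per crisis, and says that scoring covers "the choice of appropriate medications with their respective doses". The rater is blinded to group and "previously trained in the detection of errors by one of the authors".

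Annex 1, unanticipated difficult airway, step 7, reads "Application of neuromuscular relaxant at full dose (rocuronium 1.2 mg / kg dose or succinylcholine at 1.5mg IV".

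Three other places set the reach of that line:

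- Section 11a, on recording for outcome measurement: "Three crises will be carried out at random, different from those used in training to avoid cognitive continuity bias".
- Section 18: "The outcome variables will be carried out electronically and are summarized in Table 8". The table gives an electronic form based on the video. The form itself is not in the document.
- Table 6, difficult airway: the last minimum action is "Use second-generation supraglottic after laryngoscopy failure". No relaxant is listed for this crisis.

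**The concern.** Two alternatives for one criterion sit on different bases. Rocuronium scales with weight and succinylcholine does not. Annex 1 is the scoring key, so this is a working threshold and not background text. No other section gives a succinylcholine dose, and no simulated patient weight is stated, so a rater cannot resolve the line from the document.

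A rater who treats 1.5 mg as the exact dose would mark a weight-based succinylcholine dose as an omission and pass a fixed 1.5 mg. A wrongly failed step could also reach crisis resolution time, because section 12.2a says: "In the event that the treatment steps are not fully completed, the time will be measured until the end of the simulation".

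**Working it through.** The plan gives no figure of its own on this point. The check covers the dose basis, the reach of the line, and its effect on the planned difference.

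**Dose basis.** Weight is not in the document, so 50 to 90 kg is assumed. If 1.5 mg/kg was meant, the dose is 1.5 × 50 = 75 mg, 1.5 × 70 = 105 mg, or 1.5 × 90 = 135 mg. The printed 1.5 mg equals 0.030, 0.021 and 0.017 mg/kg at those weights. The two readings differ by a factor equal to the weight in kilograms.

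**Reach.** Annex 1 lists 11 crises × 7 steps = 77 steps, and one is affected. Each student is scored on 3 × 7 = 21 steps. The chance of meeting the airway crisis depends on a draw that the plan does not fully specify:

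- (a) Three of the 11 crises drawn equally for each student: 3/11 = 0.273. Removing four training crises from the same 11 first gives the same result, 7/11 × 3/7.
- (b) Four training crises drawn from the ten in section 11a (the two arrest rhythms counted separately, eight of the ten matched to Annex 1), then three test crises from the untrained remainder of Annex 1: 6/10 × [21/126 × 3/9 + 70/126 × 3/8 + 35/126 × 3/7] = 0.6 × 0.383 = 0.230.
- (c) One common draw for all students that includes the airway crisis: 1.

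Of the 28 students planned per arm, (a) gives 28 × 0.273 = 7.6, (b) gives 28 × 0.230 = 6.4, and (c) gives 28. The affected share of scored steps is 0.273/21 = 1.30%, 0.230/21 = 1.09%, and 1/21 = 4.76%.

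**Planned difference.** Section 14 assumes 26% and 16%. Let *f* be the affected share of steps and *s* the share of students choosing succinylcholine, taken as equal in both arms. If each such dose is failed, a proportion *p* becomes *p* + *f·s*(1 − *p*), and the difference becomes 10 × (1 − *f·s*) points.

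| *s* | (a) | (b) | (c) |
|---|---|---|---|
| 1 | 9.87 | 9.89 | 9.52 |
| 0.5 | 9.94 | 9.95 | 9.76 |
| 0.25 | 9.97 | 9.97 | 9.88 |

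Check of (a) at *s* = 1: 0.26 + 0.0130 × 0.74 = 0.2696 and 0.16 + 0.0130 × 0.84 = 0.1709, a difference of 9.87 points. If the rater reads the dose as per kilogram, the difference stays at 10. The document gives no value for *s*.

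**Crisis resolution time.** Each arm has 28 × 3 = 84 test crises. Under draw (a), 84/11 = 7.6 are airway crises. With *s* = 1, the clock is wrongly extended in crises where all seven steps were in fact done:

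- Independent steps: 7.6 × 0.74⁷ = 7.6 × 0.122 = 0.9 control crises, and 7.6 × 0.84⁷ = 7.6 × 0.295 = 2.3 intervention crises.
- Fully correlated steps: 7.6 × 0.74 = 5.7 and 7.6 × 0.84 = 6.4.

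A common draw would raise these counts, so none of them is a bound.

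**The case against.** The strongest reply is that this is damaged text and not a fault in the trial. The English file is a translation, and weight-based units are broken elsewhere in the same annex. In malignant hyperthermia, the dantrolene dose has a per-kilogram unit but no number. In hypovolemic shock, step 5 gives the fluid bolus per kilo, while the repeat bolus in step 7 has the unit garbled. A lost per-kilogram unit fits that pattern. The words about full dose and the weight-based alternative beside it also point a trained rater to the intended meaning, and then nothing is misscored.

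Most of this stands. It makes the practical effect probably close to zero, and it makes singling out one line too narrow. It does not make the printed line right. The sentence reads whole, with no visible gap, and no rule tells the rater to depart from a printed dose. Neither the original-language key nor the electronic form is available to settle the matter.

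A reader might go further and infer that the primary result would be biased in favor of the intervention, or that power is materially harmed. The documents do not support either. The key is the same in both arms, the rater is blinded, and with equal succinylcholine use literal scoring only shrinks the difference. A reader might also infer that the investigators intend a wrong dose. The text shows only that the two bases differ.

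**Conclusion.** The inconsistency is certain on the page, and its effect on scoring is not. It is a minor error in the primary-outcome key: one step of 77, the same in both arms, and outside the Table 6 minimum actions for this crisis, so the relaxant line does not affect inadequate crisis management.

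Under literal scoring with every student using succinylcholine, the planned 10-point difference falls to about 9.9 with separate draws per student and to about 9.5 if all students meet the airway crisis. Rocuronium users are unaffected.

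These figures rest on assumptions: the draw of test crises, equal succinylcholine use in both arms, step 7 being omitted as often as the average step, and no student giving a fixed 1.5 mg. They illustrate size and are not limits. That 1.5 mg/kg was intended is an inference.

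**What to change.** Before the first recording, the clinical leads should check step 7 against the original-language key. Both relaxants should then be stated on the same basis, either per kilogram or as a total with the mannequin's stated weight, in Annex 1 and in the electronic scoring form. If the original key and the form are already consistent, only the English line needs correcting. Which dose is right is for the clinical leads to say.

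In the same pass, they should restore the missing dantrolene number, in Table 6 as well as Annex 1, and the garbled repeat fluid bolus in hypovolemic shock.

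The cost is a few corrected lines, with no added participants, staff or data fields. If the correction does not change how the study is run, section 25 asks only for notification to the ethics committee. If the form in use has to change, the team should confirm that route with the committee. Timing matters because a change to the key after recordings have been scored would be post hoc.
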